3.4 Withdrawal Criteria

- Withdrawal of consent for any reason
- During the course of the study, the development of an injury or illness or initiation of use of a medication which, in the opinion of [name], makes the subject's continued participation dangerous to the subject or to others, or which may affect the results.
- Failure to follow GI Labs safety guidelines
- Repeated failure to attend at scheduled visits
- Repeated failure to follow the protocol

4. Study Design and Procedures

The study is double-blind with a randomized, cross-over design.

4.1 Procedures

Visit 1: Participants willing to be considered will be invited to come to the research centre to have the study procedures explained to them and be given a copy of the consent form which they may either sign then, take away to sign at a later date, or decline to participate. Participants will be encouraged to ask any questions they may have and not to sign the consent form until all of their questions have been answered to their satisfaction. Those who consent to participate will come to the research centre for a pre-selection visit when subject eligibility will be determined. A number of parameters will be assessed: including blood pressure; weight, height, BMI, and brief medical history.

Visit 2-3: Eligible subjects will be randomized using an online randomization calculator. Eligible subjects will be studied on 2 separate days over a period of 4 weeks or less. Prior to each test meal they will be provided with enough cookies to consume 3 times/day over 3 days and instructed to start consuming these 3 days before their visit. They will also be provided with a calorie appropriate, standard dinner to be consumed on the evening before their test meal. The interval between successive tests will be no less than 6 days and no more than 4 weeks. On each test day, participants will come to GI Labs in the morning after a 10-12h overnight fast (except for water). Participants will be asked to maintain stable dietary and activity habits throughout their participation and refrain from drinking alcohol and from unusual levels of food intake or physical activity for 24h before each test. Before the start of the test meal, subjects will be asked whether they consumed the provided cookies over the last 3 days as instructed and the standard dinner the evening before. Subjects will be asked to complete a 3d record of supplement consumption and whether they consumed the standard evening meal, in addition to a 3d symptom diary before each test visit. If any subject is not feeling well or has not complied with the preceding experimental conditions, the test will not be carried out and will be rescheduled for another day. On each test day, two fasting fingerprick blood samples will be collected at -5min and 0min. Each sample will consist of 2 vials, one for glucose analysis and one for insulin analysis (4—8 drops of blood each). Questionnaires to record satiety and GI symptoms will be administered. Participants will then be given the test food together with 250ml of water and instructed to consume this over 15minutes. Additional blood samples will be collected 15, 30, 45, 60, 90 and 120min after the start of the test meal. Satiety Questionnaires will be administered at the same time intervals. GI symptom questionnaires will be filled out at 2h in addition to fasting.

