2.2 Secondary objectives

- To compare the 2hour postprandial insulin incremental area under the curve (IAUC) after the Fibersym containing carbohydrate load with the control meal
- To compare the individual postprandial glucose and insulin responses at each time point after the Fibersym containing carbohydrate load with the control meal
- To compare the GI symptoms after the three days of pre-feeding of Fibersym cookies with the control meal
- To compare the satiety scores after the Fibersym containing carbohydrate load with the control meal
- SAFETY: GI symptoms and Adverse events.

3. Subject Selection

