4.5 GI Tolerability

GI tolerability will be assessed using a Physical Comfort Questionnaire (Appendix 2). Subjects will be asked to complete the Questionnaire before they start consuming the test food and every day during the 3 day pre-feeding period. During the test day, they will fill it out before consuming the test breakfast at 0min and again at 2h.

Participants mark either “yes” or “no” after each marker of physical comfort. If they mark “yes” they are instructed to rate the severity of the side-effect on a 100 mm VAS and to provide any comments they feel are necessary. The physical comfort scale includes bloating, belching, diarrhea, flatulence, nausea, headache, and a category for “other”. In the “other” category, participants will be asked to specify what they mean by “other” and rate the severity using the 100 mm line.

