7.5 Risks

No adverse events related to ingestion of the RS4 tested in this study have been reported. However, there may be rare occurrences of study product intolerance, as manifested by gastrointestinal symptoms (such as crampy gas, bloating, or watery stools), eczema, rashes, or other signs of allergy.

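### The rescheduling rule can remove symptomatic test days from the GI-symptom comparison, and the plan does not say that symptom records from cancelled attempts are kept and analysed

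*Combined protocol and SAP*

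**What the plan says.** Section 2.2 lists a secondary objective, "To compare the GI symptoms after the three days of pre-feeding of Fibersym cookies with the control meal", and then names the same symptoms again under "SAFETY: GI symptoms and Adverse events".

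Section 4.5 sets two kinds of collection point for the Physical Comfort Questionnaire. The first is during pre-feeding: "Subjects will be asked to complete the Questionnaire before they start consuming the test food and every day during the 3 day pre-feeding period". The second is at the test visit: "During the test day, they will fill it out before consuming the test breakfast at 0min and again at 2h". The flow chart in Section 4.2 marks the questionnaire in both pre-feeding periods and at both test visits. Section 4.1 adds a 3-day symptom diary before each test visit.

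Section 4.1 also holds the rescheduling rule: "If any subject is not feeling well or has not complied with the preceding experimental conditions, the test will not be carried out". The synopsis repeats it. In Section 4.1 the rule comes after the compliance check and before the fasting samples and the test-day questionnaires.

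Section 7.5 allows for occasional "study product intolerance, as manifested by gastrointestinal symptoms (such as crampy gas, bloating, or watery stools". Section 3.4 lists "Repeated failure to follow the protocol" as a withdrawal criterion, and Section 7.3 adds taking too long to complete the study.

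Section 5.1 leaves the GI-symptom calculations to be added.

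**The concern.** Whether a test goes ahead depends partly on how the subject feels after three days on the assigned cookies. If Fibersym causes symptoms, more Fibersym than control mornings may be postponed for that reason. The 0-min and 2-h scores are then not taken on the symptomatic morning, and the scores that exist come from a later and probably better day.

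The compliance half of the rule can work the same way. A subject who stops eating the cookies because of symptoms has not complied and is rescheduled. If this happens repeatedly, the subject may be withdrawn.

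Blinding does not protect against this. The decision can be made without knowing the product and still depend on an effect of the product. At stake is a tolerability result that looks closer to control than it should, in a trial of 15 subjects where one or two postponed mornings carry weight.

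**Working it through.** The plan states no figure for GI symptoms (no expected rate, SD or power), so there is none to reproduce. The check has two parts.

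**1. Which records depend on the test going ahead**

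| GI record, per period (Section 4.5) | Number | Taken before the decision to test? |
|---|---|---|
| Before starting the test food | 1 | Yes |
| Each pre-feeding day | 3 | Yes |
| Test day, 0 min | 1 | No |
| Test day, 2 h | 1 | No |

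- Share taken before the decision: 3/(3 + 2) = 60%, or 4/(4 + 2) = 67% counting the pre-start record.
- The two remaining records are the only ones scheduled after all three pre-feeding days, and the 2-h record is the only one after the test meal.
- Section 4.1 requires three days of cookies and a diary before each test. A rescheduled test may therefore produce a second set of pre-feeding records. The plan does not say whether pre-feeding is repeated, whether the set from the cancelled attempt is kept, or which set is analysed.

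**2. Possible size, test-day records only**

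The documents give no rates, so every input here is an assumption:

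- p = true chance of symptoms on a test morning
- c = chance that a symptomatic subject's test is cancelled, the same for both products
- each rescheduled morning is a fresh, independent draw, repeated until a test goes ahead

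An attempt ends in a test with symptoms with probability p(1 − c), and in any test with probability 1 − pc. So the observed symptom rate = p(1 − c)/(1 − pc).

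For p = 30% on Fibersym, 10% on control and c = 0.5:

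- Fibersym: 0.30 × 0.5/(1 − 0.15) = 0.15/0.85 = 17.6%
- Control: 0.10 × 0.5/(1 − 0.05) = 0.05/0.95 = 5.3%
- Observed difference: 12.4 points (from unrounded rates), against a true 20

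| Assumed true rates | True difference | c = 25% | c = 50% | c = 75% | c = 100% |
|---|---|---|---|---|---|
| 20% vs 10% | 10 | 8.1 | 5.8 | 3.2 | 0 |
| 30% vs 10% | 20 | 16.6 | 12.4 | 7.0 | 0 |
| 50% vs 10% | 40 | 35.2 | 28.1 | 17.3 | 0 |

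(Observed difference in percentage points.)

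With p = 30% and c = 0.5, the expected number of first Fibersym tests cancelled is 15 × 0.30 × 0.5 = 2.25. The chance of at least one is 1 − (1 − 0.15)^15 = 91%. Under these assumptions the rule would probably be used.

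**The case against.** A reader might infer that GI symptoms are compared only on days when subjects tolerated the product. The documents do not support that. Questionnaires are completed on every pre-feeding day, with a 3-day diary, so most of the scheduled records precede the decision to test. The day-3 questionnaire may come close to the end of pre-feeding; its time of day is not given.

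A reader might also infer that the rule erases the whole product difference. That holds only at c = 100%, and then only for test-day records. Nothing says that every symptomatic subject is postponed. Not feeling well is undefined, mild bloating may not trigger the rule, and the 100 mm severity scale exists to grade symptoms in subjects who are tested. Unrelated illness or a missed standard dinner also triggers the rule, and neither is selection on tolerability. If pre-feeding is repeated, symptoms may recur on the rescheduled day. That would weaken the attenuation or turn it into repeated postponement.

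Other routes capture symptoms. Section 7.4 counts any symptom as an adverse event and assesses events at each visit. Section 7.3 requires final assessments and a recorded main reason for each withdrawal.

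All of this limits the size of the problem but does not remove it. The daily records help only if those from a cancelled attempt enter the analysis, which is unstated. It is also unstated whether a cancelled attendance counts as a visit for adverse events, and the flow chart as reproduced shows no adverse-event check in the first pre-feeding period. Withdrawal reasons are recorded, but no tabulation by product is planned, and none is planned for postponements.

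**Conclusion.** The point holds for the 0-min and 2-h records. A stated rule selects which of them exist on a condition the product may cause, and the resulting bias in the product comparison is toward no difference. For the pre-feeding records it is an open gap rather than a demonstrated bias. They are a safeguard if records from cancelled attempts are analysed. If only the set attached to the completed test is used, the same selection extends to them.

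The size cannot be fixed from the documents. In the central example (30% vs 10%), a true 20-point difference shows as 16.6 to 7.0 points for cancellation chances of 25% to 75%. This rests on assumed rates, an equal cancellation chance for both products and independent draws on rescheduled days. The glucose endpoint is outside this point. Label: cheap improvement.

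**What to change.** Leave the rescheduling rule unchanged for the glucose test, and add the following:

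- **(a) Section 4.5:** a subject who attends and is postponed completes the existing Physical Comfort Questionnaire that morning.
- **(b) Section 5.1, when the GI-symptom calculations are written and before unblinding:** the analysis includes the pre-feeding and postponed-morning records from all attempts, by product, with a stated way of combining several attempts by one subject. A sensitivity analysis is restricted to completed, compliant attempts.
- **(c) Section 5.2:** postponements and withdrawals are tabulated by product with the reason (symptoms, uneaten cookies, other).

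The cost is some wording and one extra form on a postponed day. Including all attempts brings in some records with incomplete cookie intake, which dilutes exposure for an objective defined after three days of pre-feeding; the sensitivity analysis addresses that. Fibersym tolerability may look less favourable.

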4.2 Study Flow Chart

Visits Procedures	Screening	TEST VISITS				
	V1	3 day prefeeding	V2 Test meal	7 day wash out	3 day prefeeding	V3 Test meal
Informed Consent Process and Informed Consent Form Signature	X					
Subject's demographic data	X					
Inclusion and exclusion criteria	X					
Subject's eligibility	X					
Anthropometry	X		X			X
Check of dietary compliance		X	X		X	X
Record of supplement consumption		X			X	
Check of concomitant medications	X		X			X
2 Fasting blood samples			X			X
Consumption of test food			X			X
Postprandial blood samples 15, 30, 45, 60, 90 and 120min after starting to eat		X	X		X	X
GI Symptom Questionnaire		X	X		X	X
Satiety Questionnaire			X			X
Check of adverse events	X		X		X	X

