CRITERIA FOR EVALUATION:	
EFFICACY: Primary outcome is comparison of the glucose IAUC of the Fibersym meal with the control meal.
 
Secondary outcomes: comparison of the insulin (IAUC) of the Fibersym meal with the control meal, comparison of glucose and insulin levels at each time point and satiety scores at each time point.
 
SAFETY: Adverse events.

STATISTICAL METHODS:	Results for all foods in a series will be compared by GLM ANOVA. After demonstrating significant heterogeneity, the significance of the differences will be tested using Tukey method to adjust for multiple comparisons
Ethics Board Approval	The investigator will be responsible for submission of the study to the Western Institutional Research Board. Prior to submission of the application, the sponsors and all co-investigators will be given the opportunity to review the application. Submission of the application will only take place if all parties agree. The Western Institutional Review Board® meets all requirements of the US Food and Drug Administration (FDA), the Department of Health and Human Services (DHHS), the Canadian Health Protection Branch (HPB), Canadian Institutes of Health Research (CIHR) and the European Community Guidelines. Participants will not be enrolled into the study until they have had the study procedures explained to them, had a chance to ask questions, and given their voluntary consent by signing the consent form. Participants who do not understand English will not be enrolled.
Subject Selection Criteria	
Inclusion criteria:
 
 1. Male or non-pregnant females, 18-75 years of age, inclusive 2. Body mass index (BMI) between 18.5 and 35 kg/m² inclusive at screening. 3. Systolic blood pressure < 130mmHg, Diastolic Blood pressure <90mmHg. 4. Willing to maintain habitual diet, physical activity pattern, and body weight throughout the trial. 5. Subject is willing to abstain from strenuous exercise, or consume alcoholic drinks 24hours before study days. 6. Absence of health conditions that would prevent fulfillment of study requirements as judged by the Investigator on the basis

of medical history.

7. Understanding the study procedures and willing to provide informed consent to participate in the study and authorization to release relevant protected health information to the study investigator.
8. Female subjects are willing to use a contraceptive method to avoid pregnancy during the study period.

Exclusion criteria:

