4.7 Randomization

Eligible subjects will be randomized using an online randomization calculator. Orders will be assigned to subjects in the order they attend the first visit after being recruited.

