7.4 Adverse Event Reporting

An adverse event is any symptom, injury, illness, or medical/surgical procedure whether planned or not or whether associated with the study foods or not. Adverse events will be assessed at each visit and recorded in the Case Report Forms. Adverse events will be evaluated for duration, severity, seriousness, and causal relationship to the food items provided in the study by the study physician who will decide if any action is required and provide referral, treatment, and/or follow-up as appropriate until resolved, judged to no longer be clinically significant, or if a chronic condition, until fully characterized. Research staff will record the final outcome and resolution date of the event wherever possible. The action taken and the outcome will be recorded in the Case Report Form.

- It is anticipated that participants enrolled in the study will be clinically managed without the need to add medications or to change the dosage(s) assigned to their current medications. In the event that additional medication is required, or an increase in their medication dosage is warranted, these changes will be recorded as adverse events.
- Investigators are required to report adverse events that fit the following criteria within 10 working days of the time the investigator becomes aware of them:
 - Event is Unexpected (in terms of nature, severity, or frequency) given (a) the research procedures that are described in the protocol-related documents, such as the IRB-approved research protocol and informed consent document, or the Investigator Brochure; and (b) the characteristics of the subject population being studied.
 - Related or possibly related to participation in the research (possibly related means there is a reasonable possibility that the incident, experience, or outcome may have been caused by the procedures involved in the research); and
 - Suggests that the research places subjects or others at a greater risk of harm (including physical, psychological, economic, or social harm) than was previously known or recognized.

If the adverse event is clearly not related to the study drug, device, procedures, or washout process, it would not represent a risk to other subjects in the research or a “problem” for the study and, therefore, does not have to be reported to WIRB.

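### Minor: the flow chart checks adverse events in the second pre-feeding period but not the first, which does not match section 7.4, and no contact is scheduled after visit V3

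*Combined protocol and SAP*

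**What the plan says.** The synopsis, under criteria for evaluation, gives the safety outcome as "SAFETY: Adverse events". Section 2.2 is wider: "SAFETY: GI symptoms and Adverse events".

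The flow chart in section 4.2 has six columns: V1, first pre-feeding, V2, washout, second pre-feeding, V3. The row "Check of adverse events" is marked at V1, V2, second pre-feeding and V3. The first pre-feeding and washout cells are empty, and the chart ends at V3.

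The text rule is in section 7.4: "Adverse events will be assessed at each visit and recorded in the Case Report Forms". It mentions no check during pre-feeding and no new contact after V3. Its follow-up to resolution applies to events already reported.

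GI symptoms are handled separately. Section 4.5 has the Physical Comfort Questionnaire completed "every day during the 3 day pre-feeding period", and on test days section 4.1 says "GI symptom questionnaires will be filled out at 2h in addition to fasting". The chart marks this questionnaire in both pre-feeding periods and at both test visits.

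On timing, section 4.1 states: "The interval between successive tests will be no less than 6 days and no more than 4 weeks". On allocation, section 4.7 says "Eligible subjects will be randomized using an online randomization calculator", with no mention of blocking or of equal numbers in the two orders.

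**The concern.** Section 7.4 defines an adverse event broadly enough to include any symptom, so the number recorded depends on how often, and for how long, subjects are asked. In a two-period crossover the asking should be the same in each period. Here the chart adds a check while the second product is being eaten and has none while the first is being eaten. The time after each test meal in which a new event could be reported also differs.

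Two consequences follow. If the two orders are unequally filled, a difference by period becomes in part a difference by product. And an event first reported in the second pre-feeding period, or at V3, may have begun after V2, under or after the first product. The plan has no explicit rule that assigns events to a product by onset date.

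**Working it through.** The plan states no figure for this point, so the check is a comparison of schedules followed by a count.

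**1. Checks during exposure to each product (section 4.2)**

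| Chart row | Pre-feeding 1 | V2 | Pre-feeding 2 | V3 |
|---|---|---|---|---|
| Adverse events | – | X | X | X |
| GI symptom questionnaire | X | X | X | X |
| Dietary compliance | X | X | X | X |
| Supplement record | X | – | X | – |
| Concomitant medications | – | X | – | X |
| Satiety questionnaire | – | X | – | X |
| Postprandial bloods | X | X | X | X |

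Period 1 has one adverse-event check and period 2 has two. Of the rows shown, only the adverse-event row differs between periods. The remaining rows with marks in the product periods (anthropometry, fasting samples, test food) are also symmetric.

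**2. Time after each test meal in which a new event can still be reported**

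- After the V2 meal: until V3, which is 6 to 28 days later (section 4.1), or 7 + 3 = 10 days if the chart's washout and pre-feeding lengths are followed. The minimum is 6 × 24 = 144 h. The marked second pre-feeding check may fall earlier within that time.
- After the V3 meal: until the end of the visit, about 2 h, since the last sample and questionnaire are at 120 min. This assumes that the V3 check is made at the end of the visit; the plan does not say when in the visit it is made.

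**3. How far this reaches the product comparison**

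Inputs: 15 subjects (section 3.1), all assumed to complete both periods. Each subject has one visit check per product, so each product has 15. The extra check goes to whichever product the subject eats second. If *m* subjects eat product A second:

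- checks for A = 15 + *m*
- checks for B = 15 + (15 − *m*)

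| Order split | Checks, A | Checks, B | Ratio |
|---|---|---|---|
| 8:7 | 15 + 8 = 23 | 15 + 7 = 22 | 1.05 |
| 10:5 | 15 + 10 = 25 | 15 + 5 = 20 | 1.25 |

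How likely is an unequal split? The documents do not give the allocation method. Under simple 1:1 randomisation, which is an assumption, the split follows Binomial(15, 0.5):

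- 10:5 or worse: 2 × 4944/32768 = 0.302
- 11:4 or worse: 2 × 1941/32768 = 0.118

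If the calculator balances the orders, the split is close to 8:7 and the difference is one check.

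These are counts of scheduled opportunities to report, not of events. The plan gives no adverse-event rate, so a bias in event counts cannot be computed.

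**The case against.** The strongest reply is that one mark in a table is being read as an operating plan. The same chart marks postprandial blood samples in both pre-feeding columns, although section 4.1 takes them only on test days, so its marks are not wholly reliable. Section 7.4 gives a rule that is the same for both periods, and section 4.1 describes no adverse-event contact during either pre-feeding period. This stands as a reason to grade the point low: the extra mark may well be a slip. It does not remove the need to correct it, because staff who follow the chart would carry out the extra check.

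Four stronger readings are tempting, and the documents do not support them.

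- *That safety as a whole is collected unequally.* Section 2.2 includes GI symptoms, and these are recorded on the same schedule in both periods. The questionnaire also has an open item for other symptoms. Only the adverse-event part is affected. That part still matters for the skin and allergic signs named in section 7.5, which have no line of their own on the Appendix 2 form.
- *That events in the first pre-feeding period are lost.* They can be reported by recall at V2, which follows directly.
- *That one cookie could be checked twice as often.* At 10:5 that is true of the extra check alone (10 versus 5). With the visit checks included, the totals are 25 versus 20.
- *That nothing is asked after the last test meal.* V3 itself has a check, which could fall after the meal. What the documents show is that no contact is scheduled after visit V3.

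On attribution, section 7.4 already has the study physician judge duration and causal relationship, which helps. It stops short of a stated onset-date rule, and uncertainty about events arising after V2 would exist at V3 even without the extra check.

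**Conclusion.** The point holds as a minor one. Sections 4.2 and 7.4 do not agree on when adverse events are asked about. Followed as written, the chart gives one check during exposure in period 1 and two in period 2. New events can be reported for at least 144 h after the V2 meal but for only about 2 h after the V3 meal.

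The effect on the product comparison is indirect and probably small: a difference of one check at the best split, five at 10:5, and whatever late events are assigned to the wrong product. The 30% chance of a split of 10:5 or worse depends wholly on the simple-randomisation assumption. Section 5.2 plans safety summaries and specifies no between-product adverse-event test, which limits the consequence further. The primary glucose outcome and the GI-symptom data are not touched.

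**What to change.** - **Reconcile 4.2 with 7.4.** Put the pre-feeding adverse-event check in both periods, with the same question and timing, or in neither. Each product then has 30 checks (both) or 15 (neither) whatever the order split, so order imbalance no longer matters for this count.
- **Use the same post-test window after V2 and V3.** One brief call after each, at the same interval, would do.
- **State in 7.4 that each event is assigned to a product by its onset date,** and record that date on the case report form.
- **Correct the chart's other misplaced marks at the same time,** namely the postprandial blood samples in the two pre-feeding columns.

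The cost is a few chart cells and a sentence or two in 7.4. The only real burden is one or two short contacts per subject if the calls are adopted. Neither the feeding schedule nor the primary analysis needs to change.
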